12.2 Disease Parameters

Measurable disease: Measurable lesions are defined as those that can be accurately measured in at least one dimension (longest diameter to be recorded) as >20 mm by chest x-ray, as >10 mm with CT scan, or >10 mm with calipers by clinical exam. All tumor measurements must be recorded in millimeters (or decimal fractions of centimeters).

Malignant lymph nodes: To be considered pathologically enlarged and measurable, a lymph node must be >15 mm in short axis when assessed by CT scan (CT scan slice thickness recommended to be no greater than 5 mm). At baseline and in follow-up, only the short axis will be measured and followed.

Non-measurable disease: All other lesions (or sites of disease), including small lesions (longest diameter <10 mm or pathological lymph nodes with ≥10 to <15 mm short axis), are considered non-measurable disease. Bone lesions, leptomeningeal disease, ascites, pleural/pericardial effusions, lymphangitis cutis/pulmonitis, inflammatory breast disease, and abdominal masses (not followed by CT or MRI), are considered as non-measurable.

Note: Cystic lesions that meet the criteria for radiographically defined simple cysts should not be considered as malignant lesions (neither measurable nor non-measurable) since they are, by definition, simple cysts.

Protocol Version: 02/02/24 Page 34 of 57

'Cystic lesions' thought to represent cystic metastases can be considered as measurable lesions, if they meet the definition of measurability described above. However, if non-cystic lesions are present in the same patient, these are preferred for selection as target lesions.

Target lesions: All measurable lesions up to a maximum of 2 lesions per organ and 5 lesions in total, representative of all involved organs, should be identified as target lesions and recorded and measured at baseline. Target lesions should be selected on the basis of their size (lesions with the longest diameter), be representative of all involved organs, but in addition should be those that lend themselves to reproducible repeated measurements. It may be the case that, on occasion, the largest lesion does not lend itself to reproducible measurement in which circumstance the next largest lesion which can be measured reproducibly should be selected. A sum of the diameters (longest for non-nodal lesions, short axis for nodal lesions) for all target lesions will be calculated and reported as the baseline sum diameters. If lymph nodes are to be included in the sum, then only the short axis is added into the sum. The baseline sum diameters will be used as reference to further characterize any objective tumor regression in the measurable dimension of the disease.

Non-target lesions: All other lesions (or sites of disease) including any measurable lesions over and above the 5 target lesions should be identified as non-target lesions and should also be recorded at baseline. Measurements of these lesions are not required, but the presence, absence, or in rare cases unequivocal progression of each should be noted throughout follow-up.

12.3 Methods for Evaluation of Measurable Disease

All measurements should be taken and recorded in metric notation using a ruler or calipers. All baseline evaluations should be performed as closely as possible to the beginning of treatment and never more than 4 weeks before the beginning of the treatment.

The same method of assessment and the same technique should be used to characterize each identified and reported lesion at baseline and during follow-up. Imaging-based evaluation is preferred to evaluation by clinical examination unless the lesion(s) being followed cannot be imaged but are assessable by clinical exam.

Clinical lesions: Clinical lesions will only be considered measurable when they are superficial (e.g., skin nodules and palpable lymph nodes) and ≥10 mm diameter as assessed using calipers (e.g., skin nodules). In the case of skin lesions, documentation by color photography, including a ruler to estimate the size of the lesion, is recommended.

Chest x-ray: Lesions on chest x-ray are acceptable as measurable lesions when they are clearly defined and surrounded by aerated lung. However, CT is preferable.

Conventional CT and MRI: This guideline has defined measurability of lesions on CT scan based on the assumption that CT slice thickness is 5 mm or less. If CT scans have slice

Protocol Version: 02/02/24 Page 35 of 57

thickness greater than 5 mm, the minimum size for a measurable lesion should be twice the slice thickness. MRI is also acceptable in certain situations (e.g. for body scans).

Use of MRI remains a complex issue. MRI has excellent contrast, spatial, and temporal resolution; however, there are many image acquisition variables involved in MRI, which greatly impact image quality, lesion conspicuity, and measurement. Furthermore, the availability of MRI is variable globally. As with CT, if an MRI is performed, the technical specifications of the scanning sequences used should be optimized for the evaluation of the type and site of disease. Furthermore, as with CT, the modality used at follow-up should be the same as was used at baseline and the lesions should be measured/assessed on the same pulse sequence. It is beyond the scope of the RECIST guidelines to prescribe specific MRI pulse sequence parameters for all scanners, body parts, and diseases. Ideally, the same type of scanner should be used and the image acquisition protocol should be followed as closely as possible to prior scans. Body scans should be performed with breath-hold scanning techniques, if possible.

PET-CT: At present, the low dose or attenuation correction CT portion of a combined PET-CT is not always of optimal diagnostic CT quality for use with RECIST measurements. However, if the site can document that the CT performed as part of a PET-CT is of identical diagnostic quality to a diagnostic CT (with IV and oral contrast), then the CT portion of the PET-CT can be used for RECIST measurements and can be used interchangeably with conventional CT in accurately measuring cancer lesions over time. Note, however, that the PET portion of the CT introduces additional data which may bias an investigator if it is not routinely or serially performed.

Ultrasound: Ultrasound is not useful in assessment of lesion size and should not be used as a method of measurement. Ultrasound examinations cannot be reproduced in their entirety for independent review at a later date and, because they are operator dependent, it cannot be guaranteed that the same technique and measurements will be taken from one assessment to the next. If new lesions are identified by ultrasound in the course of the study, confirmation by CT or MRI is advised. If there is concern about radiation exposure at CT, MRI may be used instead of CT in selected instances.

Endoscopy, Laparoscopy: The utilization of these techniques for objective tumor evaluation is not advised. However, such techniques may be useful to confirm complete pathological response when biopsies are obtained or to determine relapse in trials where recurrence following complete response (CR) or surgical resection is an endpoint.

Tumor markers: Tumor markers alone cannot be used to assess response. If markers are initially above the upper normal limit, they must normalize for a patient to be considered in complete clinical response. Specific guidelines for both CA-125 response (in recurrent ovarian cancer) and PSA response (in recurrent prostate cancer) have been published.³³⁻³⁵ In addition, the Gynecologic Cancer Intergroup has developed CA-125 progression criteria which are to be integrated with objective tumor assessment for use in first-line trials in ovarian cancer.³⁶

Protocol Version: 02/02/24 Page 36 of 57

Cytology, Histology: These techniques can be used to differentiate between partial responses (PR) and complete responses (CR) in rare cases (e.g., residual lesions in tumor types, such as germ cell tumors, where known residual benign tumors can remain).

The cytological confirmation of the neoplastic origin of any effusion that appears or worsens during treatment when the measurable tumor has met criteria for response or stable disease is mandatory to differentiate between response or stable disease (an effusion may be a side effect of the treatment) and progressive disease.

FDG-PET: While FDG-PET response assessments need additional study, it is sometimes reasonable to incorporate the use of FDG-PET scanning to complement CT scanning in assessment of progression (particularly possible 'new' disease). New lesions on the basis of FDG-PET imaging can be identified according to the following algorithm:

- Negative FDG-PET at baseline, with a positive FDG-PET at follow-up is a sign of PD based on a new lesion.
- No FDG-PET at baseline and a positive FDG-PET at follow-up: If the positive FDG-PET at follow-up corresponds to a new site of disease confirmed by CT, this is PD. If the positive FDG-PET at follow-up is not confirmed as a new site of disease on CT, additional follow-up CT scans are needed to determine if there is truly progression occurring at that site (if so, the date of PD will be the date of the initial abnormal FDG-PET scan). If the positive FDG-PET at follow-up corresponds to a pre-existing site of disease on CT that is not progressing on the basis of the anatomic images, this is not PD.
- FDG-PET may be used to upgrade a response to a CR in a manner similar to a biopsy in cases where a residual radiographic abnormality is thought to represent fibrosis or scarring. The use of FDG-PET in this circumstance should be prospectively described in the protocol and supported by disease-specific medical literature for the indication. However, it must be acknowledged that both approaches may lead to false positive CR due to limitations of FDG-PET and biopsy resolution/sensitivity.

Note: A 'positive' FDG-PET scan lesion means one which is FDG avid with an uptake greater than twice that of the surrounding tissue on the attenuation corrected image.

12.4 Response Criteria

12.4.1 Evaluation of Target Lesions

Complete Response (CR): Disappearance of all target lesions. Any pathological lymph nodes (whether target or non-target) must have reduction in short axis to <10 mm.

Partial Response (PR): At least a 30% decrease in the sum of the diameters of target lesions, taking as reference the baseline sum diameters.

Protocol Version: 02/02/24 Page 37 of 57

Progressive Disease (PD): At least a 20% increase in the sum of the diameters of target lesions, taking as reference the smallest sum on study (this includes the baseline sum if that is the smallest on study). In addition to the relative increase of 20%, the sum must also demonstrate an absolute increase of at least 5 mm. (Note: the appearance of one or more new lesions is also considered progressions).

Stable Disease (SD): Neither sufficient shrinkage to qualify for PR nor sufficient increase to qualify for PD, taking as reference the smallest sum diameters while on study.

12.4.2 Evaluation of Non-Target Lesions

Complete Response (CR): Disappearance of all non-target lesions and normalization of tumor marker level. All lymph nodes must be non-pathological in size (<10 mm short axis).

Note: If tumor markers are initially above the upper normal limit, they must normalize for a patient to be considered in complete clinical response.

Non-CR/Non-PD: Persistence of one or more non-target lesion(s) and/or maintenance of tumor marker level above the normal limits.

Progressive Disease (PD): Appearance of one or more new lesions and/or unequivocal progression of existing non-target lesions. Unequivocal progression should not normally trump target lesion status. It must be representative of overall disease status change, not a single lesion increase.

Although a clear progression of "non-target" lesions only is exceptional, the opinion of the treating physician should prevail in such circumstances, and the progression status should be confirmed at a later time by the review panel (or Principal Investigator).

12.4.3 Evaluation of Best Overall Response

The best overall response is the best response recorded from the start of the treatment until disease progression/recurrence (taking as reference for progressive disease the smallest measurements recorded since the treatment started). The patient's best response assignment will depend on the achievement of both measurement and confirmation criteria.

Protocol Version: 02/02/24 Page 38 of 57

For Patients with Measurable Disease (i.e., Target Disease)

Target	Non-Target	New	Overall	Best Overall Response
Lesions	Lesions	Lesions	Response	when Confirmation is
				Required*
CR	CR	No	CR	>4 wks. Confirmation**
CR	Non-CR/Non-	No	PR	
	PD			
CR	Not evaluated	No	PR	>4 wks. Confirmation**
PR	Non-CR/Non-	No	PR	74 wks. Commination
	PD/not			
	evaluated			
SD	Non-CR/Non-	No	SD	Documented at least once
	PD/not			>4 wks. from baseline**
	evaluated			>4 wks. Holli baseille
PD	Any	Yes or	PD	
		No		
Any	PD***	Yes or	PD	no prior SD, PR or CR
		No		
Any	Any	Yes	PD	

^{*} See RECIST 1.1 manuscript for further details on what is evidence of a new lesion.

Note: Patients with a global deterioration of health status requiring discontinuation of treatment without objective evidence of disease progression at that time should be reported as "symptomatic deterioration." Every effort should be made to document the objective progression even after discontinuation of treatment.

For Patients with Non-Measurable Disease (i.e., Non-Target Disease)

Non-Target Lesions	New Lesions	Overall Response	
CR	No	CR	
Non-CR/non-PD	No	Non-CR/non-PD*	
Not all evaluated	No	not evaluated	
Unequivocal PD	Yes or No	PD	
Any	Yes	PD	

^{* &#}x27;Non-CR/non-PD' is preferred over 'stable disease' for non-target disease since SD is increasingly used as an endpoint for assessment of efficacy in some trials so to assign this category when no lesions can be measured is not advised

12.4.4 Duration of Response

Duration of overall response: The duration of overall response is measured from the time measurement criteria are met for CR or PR (whichever is first recorded)

^{**} Only for non-randomized trials with response as primary endpoint.

^{***} In exceptional circumstances, unequivocal progression in non-target lesions may be accepted as disease progression.

until the first date that recurrent or progressive disease is objectively documented (taking as reference for progressive disease the smallest measurements recorded since the treatment started).

The duration of overall CR is measured from the time measurement criteria are first met for CR until the first date that progressive disease is objectively documented.

Duration of stable disease: Stable disease is measured from the start of the treatment until the criteria for progression are met, taking as reference the smallest measurements recorded since the treatment started, including the baseline measurements.

12.4.5 Progression-Free Survival

PFS is defined as the duration of time from start of treatment to time of progression or death, whichever occurs first.

12.4.6 Response Review

It is strongly recommended that all responses be reviewed by an expert(s) independent of the study at the study's completion.

13.0 DATA AND SAFETY MONITORING

In compliance with the Washington University Institutional Data and Safety Monitoring Plan, an independent Data and Safety Monitoring Committee (DSMC) will be specifically convened for this trial to review toxicity data at least every 6 months. A DSMC will consist of no fewer than 3 members including 2 clinical investigators and a biostatistician. Like investigators, DSMC members are subject to the Washington University School of Medicine policies regarding standards of conduct. Individuals invited to serve on the DSMC will disclose any potential conflicts of interest to the trial principal investigator and/or appropriate university officials, in accordance with institution policies. Potential conflicts that develop during a trial or a member's tenure on a DSMC must also be disclosed.

The DSM report will be prepared by the study statistician with assistance from the study team, will be reviewed by the DSMC, and will be submitted to the Quality Assurance and Safety Monitoring Committee (QASMC). This report will include:

- HRPO protocol number, protocol title, Principal Investigator name, data coordinator name, regulatory coordinator name, and statistician
- Date of initial HRPO approval, date of most recent consent HRPO approval/revision, date of HRPO expiration, date of most recent QA audit, study status, and phase of study

Protocol Version: 02/02/24 Page 40 of 57

- History of study including summary of substantive amendments; summary of accrual suspensions including start/stop dates and reason; and summary of protocol exceptions, error, or breach of confidentiality including start/stop dates and reason
- Study-wide target accrual and study-wide actual accrual including numbers from participating sites
- Protocol activation date at each participating site
- Average rate of accrual observed in year 1, year 2, and subsequent years at each participating site
- Expected accrual end date
- Objectives of protocol with supporting data and list the number of participants who have met each objective
- Measures of efficacy
- Early stopping rules with supporting data and list the number of participants who have met the early stopping rules
- Summary of toxicities at all participating sites
- Abstract submissions/publications
- Summary of any recent literature that may affect the safety or ethics of the study

Further DSMC responsibilities are described in the DSMC charter.

Until such a time as the first secondary site activates this protocol, a semi-annual DSM report to be prepared by the study team will be submitted to the QASM Committee beginning 6 months after study activation at Washington University.

The study principal investigator and coordinator will monitor for serious toxicities on an ongoing basis. Once the principal investigator or coordinator becomes aware of an adverse event, the AE will be reported to the HRPO and QASMC according to institutional guidelines (please refer to Section 7.0).

Refer to the Washington University Quality Assurance and Data Safety Monitoring Committee Policies and Procedures for full details on the responsibilities of the DSMC at https://siteman.wustl.edu/wp-content/uploads/2015/10/QASMC-Policies-and-Procedures-03.31.2015.pdf

14.0 AUDITING

As coordinating center of this trial, Washington University (via the Quality Assurance and Safety Monitoring Committee (QASMC) will monitor each participating site to ensure that all protocol requirements are being met; that applicable federal regulations are being followed; and that best practices for patient safety and data collection are being followed per protocol. Participating sites will be asked to send copies of all audit materials, including source documentation. The audit notification will be sent to the Washington University Research Patient Coordinator, who will obtain the audit materials from the participating institution.

Protocol Version: 02/02/24 Page 41 of 57

Notification of an upcoming audit will be sent to the research team one month ahead of the audit. Once accrual numbers are confirmed, and approximately 30 days prior to the audit, a list of the cases selected for review (up to 10 for each site) will be sent to the research team. However, if during the audit the need arises to review cases not initially selected, the research team will be asked to provide the additional charts within two working days.

Items to be evaluated include:

- Subject screening and enrollment
- Reporting of adverse events
- Maintenance of HIPAA compliance
- Completeness of regulatory documentation
- Completeness of participant documentation
- Acquisition of informed consent
- IRB documentation
- Issues of protocol adherence

Additional details regarding the auditing policies and procedures can be found at https://siteman.wustl.edu/wp-content/uploads/2015/10/QASMC-Policies-and-Procedures-03.31.2015.pdf

15.0 STATISTICAL CONSIDERATIONS

15.1 Study Objectives and Endpoints

15.1.1 Primary Endpoint

Response rate (partial response plus complete response) after two cycles of therapy

15.1.2 Secondary Endpoints

- To evaluate progression free survival
- To correlate outcomes with specific mutations
- To further evaluate extreme responders with exome and transcriptome sequencing.
- To evaluate the mechanisms of secondary resistance

15.2 Study Design

This is an open label, single-arm pilot study to obtain preliminary information of the efficacy of single agent nintedanib. A total of 20 patients will be enrolled in this study. The sample size is determined primarily based on clinical feasibility rather than statistical power. However, the proposed sample size will provide us a reasonable precision to estimate the preliminary information. ³⁷If 4 responders are observed out of 20 patients, for example, we would have 80% confidence that the "true" rate would fall between 9% and 36%. If the

Protocol Version: 02/02/24 Page 42 of 57

"true" response rate is 20% or higher, there would be 80% chance of observing at least 3 responders out of 20 patients. Conversely, there would be <10% chance to observe 3 or more responders if the true rate is less than 5%.

15.3 Data Analysis

As a pilot study for proof of principal, the data analysis will be descriptive in nature. Demographic and clinical characteristics of the sample, as well as response, toxicity by grade and loss to follow up will be summarized using descriptive statistics. Kaplan-Meier product limit estimator will be used to describe the distribution of progression free survival. The 95% confidence interval (CI) for RR and 6-month PFS will also be calculated.

15.4 Correlative Studies Analysis

The association between response and specific mutation status will be assessed by permutation analysis. Taking the relationship between *FGFR1* expression and RR as an example, for instance, we first compute the observed test statistics, e.g., the sample mean difference between responders versus non-responders. Then to simulate the null distribution of the test statistics, or the distribution of the observed mean differences if there were truly no difference, we repeat the following 10,000 times: we randomly shuffle the response status, and then calculate the sample difference between the newly designated groups. The permutation p-value equals the proportion of simulations from the null distribution that exceed the observed test statistics.

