2.2 Secondary Objectives

- 1. To evaluate progression free survival.
- 2. To correlate outcomes with specific mutations.
- 3. To further evaluate extreme responders with exome and transcriptome sequencing.
- 4. To evaluate the mechanisms of secondary resistance.

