3.0 PATIENT SELECTION

3.1 Inclusion Criteria

1. Histologically confirmed diagnosis of advanced (metastatic or unresectable) NSCLC with mutations, rearrangement and fusion involving RET oncogene, or abnormalities (non-synonymous SNV or amplification) in the nintedanib target genes *VEGFR1-3*,

Protocol Version: 02/02/24 Page 16 of 57

- TP53, PDGFR-A, PDGFR-B, or FGFR1-3.CLIA certified lab testing for nintedanib target genes using cell free DNA from peripheral blood and/or assays performed on tumor tissues are acceptable
- 2. Patients with EGFR mutations or ALK rearrangements must have disease progression on appropriate FDA-approved therapy for these genomic aberrations prior to enrollment.
- 3. Disease progression on platinum-doublet chemotherapy prior to enrollment.
- 4. At least one measurable lesion or evaluable disease. Measurable disease is defined as lesions that can be accurately measured in at least one dimension (longest diameter to be recorded) as ≥10 mm with CT scan, as ≥20 mm by chest x-ray, or ≥10 mm with calipers by clinical exam.
- 5. Prior treatment of cancer (chemotherapy, radiation therapy, and surgery) is allowed if completed at least 3 weeks prior to start of treatment with nintedanib and if all treatment-related toxicities are resolved.
- 6. At least 18 years of age.
- 7. ECOG performance status 0-1 (see Appendix A).
- 8. Normal bone marrow and organ function as defined below:
 - a. Leukocytes $\geq 3,000/\text{mcL}$
 - b. Absolute neutrophil count ≥ 1,500/mcL
 - c. Platelets $\geq 100,000/\text{mcL}$
 - d. Hemoglobin $\geq 9.0 \text{ g/dL}$
 - e. INR < 2.0
 - f. PT and PTT < 50% of deviation from IULN
 - g. Total bilirubin $\leq 1.5 \text{ x IULN}$
 - h. $AST(SGOT)/ALT(SGPT) \le 1.5 \text{ x IULN}$ for patients without liver metastases and $\le 2.5 \text{ x IULN}$ for patients with liver metastases
 - i. Urine protein < 2+
 - j. Creatinine within normal institutional limits

Creatinine clearance > 45 mL/min for patients with creatinine levels above institutional normal

9. Women of childbearing potential and men must agree to use adequate contraception (hormonal or barrier method of birth control, abstinence) prior to study entry, for the duration of study participation, and for 3 months after the end of treatment. Should a woman become pregnant or suspect she is pregnant while participating in this study, she must inform her treating physician immediately.

Protocol Version: 02/02/24 Page 17 of 57

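### Section 15.4 counts only shuffles strictly above the observed statistic, so p-values for yes/no mutation status in 20 patients are too small, and no tail is stated

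*Combined protocol and SAP*

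**What the plan says.** Section 2.2 lists as a secondary objective: "To correlate outcomes with specific mutations". Section 15.4 gives the method: "The association between response and specific mutation status will be assessed by permutation analysis". The procedure is then illustrated with FGFR1 expression. The statistic is offered as an example, "the sample mean difference between responders versus non-responders"; response status is shuffled 10,000 times; and "The permutation p-value equals the proportion of simulations from the null distribution that exceed the observed test statistics".

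This is the only p-value rule in the documents. There is no tie rule, the observed arrangement is not added to the count, no absolute value is taken, and no tail is named.

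On context, Section 3.1 admits patients with RET alterations or "abnormalities (non-synonymous SNV or amplification) in the nintedanib target genes", findings that are naturally recorded as present or absent. Section 15.2 states: "A total of 20 patients will be enrolled in this study". Section 15.3 says that "the data analysis will be descriptive in nature", and no significance level is given for Section 15.4.

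**The concern.** A permutation p-value is the chance, under no association, of a result at least as extreme as the one observed. It must include results equal to the observed one, because the observed arrangement is itself one of the possible shuffles. Counting only larger values omits that probability.

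With FGFR1 expression the omission is trivial: in a simulated continuous example the two counts gave 0.0860 and 0.0861. With yes/no status it is not. If 4 of 20 patients respond, the number of responding carriers takes at most five values (0 to 4), so a single tied value can hold most of the tail. Any most-favourable table, such as one carrier who responds or two of two, returns exactly 0.

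The missing tail is a second gap. If the difference is used signed and only the upper tail is counted, a mutation associated with non-response produces a p-value near 1.

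At stake is the credibility of the gene-by-response results, which are a stated secondary objective and the ones most likely to be carried into later work.

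**Working it through.** **Inputs.** N = 20 and the example of R = 4 responders (Section 15.2); shuffling of response labels and the strict counting rule (Section 15.4). Carrier counts m are not in the documents, so a range is shown. The 0.05 threshold is an assumption.

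**The plan's own figure.** Section 15.2 says that with 4 of 20 responding the true rate "would fall between 9% and 36"%, at 80% confidence. The exact (Clopper-Pearson) 80% interval for 4/20 is 9.0% to 36.1%, so the figure reproduces.

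**Null distribution.** Shuffling response labels keeps R and m fixed. The number k of responding carriers is then hypergeometric:

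P(k) = C(m,k) × C(20−m, 4−k) / C(20,4).

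The statistic is T = k/4 − (m−k)/16, which rises with k. On the upper tail the rule as written is P(T* > T_obs); counting ties it is P(T* ≥ T_obs).

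**Worked cases, R = 4.**

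- m = 1, k = 1: P(1) = 4/20 = 0.200. No shuffle can be larger, so p = 0 as written; with ties, 0.200.
- m = 2, k = 1: P(1) = 0.3368 and P(2) = 0.0316. As written 0.032; with ties 0.3368 + 0.0316 = 0.368.
- m = 4, k = 2: P(2) = 0.1486 and P(3) + P(4) = 0.0134. As written 0.013; with ties 0.1486 + 0.0134 = 0.162.

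In these three cases the values on |T| are the same, so taking the absolute difference does not remove the problem. A check with 10,000 random shuffles gave 0 and 0.197 for the first case, and 0.034 and 0.365 for the second (the second value of each pair from the rule proposed below).

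**False-positive chance at an assumed 0.05.** This is the null probability of a table whose p-value is 0.05 or less. For R = 4, rule as written, upper tail:

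| Carriers | 1 | 2 | 3 | 4 | 5 | 6 | 7 | 8 | 9 | 10 | 11 | 12 | 13 | 14 | 15 |
|---|---|---|---|---|---|---|---|---|---|---|---|---|---|---|---|
| % | 20.0 | 36.8 | 8.8 | 16.2 | 24.9 | 6.1 | 10.1 | 15.3 | 21.7 | 29.1 | 6.8 | 10.2 | 14.8 | 20.7 | 28.2 |

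- The median is 16.2%.
- Over 2 to 6 responders and 1 to 15 carriers, the range is 5.1% (5 responders, 12 carriers) to 55.3% (2 responders, 15 carriers); 56 of the 75 combinations exceed 10%.
- Strict counting on |T| with R = 4 gives 6.1% to 53.0%, median 10.1%. The 53.0% occurs only at 5 and 15 carriers, where tables on opposite sides tie in |T|; the next highest is 36.8%.
- Counting ties on |T| gives 0% to 3.2% with R = 4 and never more than 5.0% over 2 to 6 responders.

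**Tail.** With m = 15 and k = 0, T = 0 − 15/16. The signed upper-tail rule gives 1 − P(0) = 0.999. The two-sided value with ties is P(0) = 0.001.

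**The case against.** The case rests on one verb in a section written by way of illustration, and its worked example is one where ties do not matter. An analyst could count ties without contradicting anything else in the plan, and some inputs, such as transcriptome measures, may be continuous. The plan does not say that mutation status will be coded yes/no. The analysis is descriptive, with no significance level and no decision attached, so a false-positive rate presupposes a threshold the plan never sets. The grid of carrier and responder counts weights every combination equally, which says nothing about the carrier counts this trial will have. A one-sided question may be intended, since Section 9.1 looks for variants that confer susceptibility. Readers would also see the raw counts, and few would be persuaded by one responding carrier.

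Much of this limits the weight of the point. The threshold-based rates are secondary, the grid is illustrative, and requiring a two-sided test is partly preference. None of it supplies a tie rule or a tail, which appear nowhere else in the documents. Present/absent is the natural coding for a variant or an amplification. A reported p of 0 for an overlap that chance produces 20% of the time is wrong whatever the threshold and however descriptive the analysis.

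**Conclusion.** The concern holds. Followed literally, Section 15.4 gives p-values that are too small for yes/no mutation status, on either the signed or the absolute difference. The result that needs no threshold is p = 0 against 0.200 for a single responding carrier with 4 responders. At an assumed 0.05, some carrier counts sit near nominal, but most of those examined do not.

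The conclusion assumes binary coding and the literal reading of the counting rule. The 0.999 against 0.001 contrast applies only if the statistic is signed and upper-tail. The primary response-rate estimate, the sample size, PFS and safety are untouched. This should be corrected before analysis, but it does not threaten the trial.

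**What to change.** Replace the p-value sentence in Section 15.4 with: The two-sided permutation p-value is (1 + number of shuffles with |T*| ≥ |T_obs|) / (10,000 + 1). These p-values are exploratory. If a one-sided question is intended, state the direction; the tie and plus-one corrections are needed either way.

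Fisher's exact test is an acceptable alternative for binary status but not an equivalent one. With 4 responders and 5 carriers, 2 of them responding, Fisher's two-sided p is 0.249 and the |T| rule gives 0.530. The plan should name one of the two before the data are analysed.

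The cost is one sentence and one line of code, with no extra patients or data. The downside is larger p-values and a plain view of how little power there is. With 4 responders, a gene carried by 1 or by 10 patients can never reach 0.05 two-sided (smallest possible 0.200 and 0.087), and an association with non-response can reach it only when 11 to 18 of the 20 patients are carriers.
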